6.2 Target sample size and rationale for calculation

The primary objective of this study is to determine whether there is a difference in the time taken to reach full oral feeding, from the initiation of oral feeding, when DST and OSMS are applied to preterm infants preparing for the transition from gavage feeding to oral feeding.

To calculate the sample size required to achieve the research objective, the following assumptions are made:

Protocol_DST and OSMS_oral feeding performance

(1) Level of significance (α): 0.0167 (two-tailed test).

When comparing the control group with the DST group, the control group with the DST + OSMS group, and the DST group with the DST + OSMS group, there is an issue of multiple comparisons. To address this, Bonferroni correction is applied. The significance level used is $0.05/3 = 0.0167$.

(2) Group ratio: Control group : DST group : DST + OSMS group = 1 : 1 : 1.

(3) Type II error (β): 0.20, maintaining a test power of 80%.

(4) Primary outcome: Days from start to full oral feeding (SOF-FOF).

(5) The hypothesis of the study is as follows:

[Hypothesis 1]

Null hypothesis: There is no difference in SOF-FOF days between the control group and the DST group.

Alternative hypothesis: There is a difference in SOF-FOF days between the control group and the DST group.

[Hypothesis 2]

Null hypothesis: There is no difference in SOF-FOF days between the control group and the DST + OSMS group.

Alternative hypothesis: There is a difference in SOF-FOF days between the control group and the DST + OSMS group.

[Hypothesis 3]

Null hypothesis: There is no difference in SOF-FOF days between the DST group and the DST + OSMS group.

Alternative hypothesis: There is a difference in SOF-FOF days between the DST group and the DST + OSMS group.

(6) Sample size calculation method: The PASS program (Power Analysis and Sample Size software; <http://www.ncss.com>) will be used.

Based on existing research data (16, 18), the average SOF-FOF days for each group were assumed as follows: Control group 20.8 days, DST group 14.6 days, and DST + OSMS group 10.0 days. The pooled standard deviation was calculated to be 7.19. With a significance level of 1.67% and a two-tailed test, the required sample size for 80% power is 56 participants per group, for a total of 168 participants.

Protocol_DST and OSMS_oral feeding performance

Assuming a 10% dropout rate, the final sample size, accounting for dropouts, is 189 participants.

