8.4.2 Statistical Analysis Methods

- Statistical Software: SPSS for Windows (version 19.0)
- Continuous Variables: Mann-Whitney U test, One-way ANOVA
- Categorical Variables: Chi-square test, Fisher's exact test
- Evaluation of the Effect of Interventions on Primary and Secondary Outcomes:
 - Two-way analysis of variance
 - Repeated measures analysis of variance
 - Post-hoc analysis, if necessary
- Univariate/Multivariate Analysis: Binary and multiple logistic regression analysis
- Unless otherwise specified, all statistical tests will be conducted at a two-sided significance level of 0.05.

9. Drop out

<Criteria for Clinical Trial Dropout>

- When the guardian requests discontinuation of the clinical trial or withdraws consent for participation.
- When the participant experiences respiratory deterioration during the trial period, requiring the use of a respiratory device beyond nasal positive pressure ventilation.
- When the participant experiences gastrointestinal deterioration during the trial period, necessitating fasting for more than 48 hours.
- When a serious adverse event occurs.

10. References

- 1) American Academy of Pediatrics Committee on Fetus and Newborn. Hospital discharge of the high-risk neonate. *Pediatrics* 2008;122:1119-26.
- 2) Bragdon DB. A basis for the nursing management of feeding the premature infant. *JOGN Nurs* 1983;12(3 Suppl):51s-7s.
- 3) Gryboski JD. Suck and swallow in the premature infant. *Pediatrics* 1969;43:96-102.
- 6) Bingham PM. Deprivation and dysphagia in premature infants. *J Child Neurol* 2009;24:743-9.

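### Bonferroni at 0.0167 gives up power on DST vs DST+OSMS that a three-arm closed procedure would recover at the same sample size; 8.4.2 also does not restate which rule applies

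*Combined protocol and SAP*

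**What the plan says.** Section 6.2 states three hypotheses on SOF-FOF days: control vs DST, control vs DST+OSMS, and DST vs DST+OSMS. The last reads "Null hypothesis: There is no difference in SOF-FOF days between the DST group and the DST + OSMS group". On multiplicity it says "there is an issue of multiple comparisons. To address this, Bonferroni correction is applied", giving 0.05/3 = 0.0167. These items belong to a list introduced by "To calculate the sample size required to achieve the research objective, the following assumptions are made", and the calculation ends with "With a significance level of 1.67% and a two-tailed test, the required sample size for 80% power is 56 participants per group".

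Section 8.4.2 does not mention Bonferroni, 0.0167 or the three hypotheses. Under "Evaluation of the Effect of Interventions on Primary and Secondary Outcomes" it lists two-way ANOVA, repeated-measures ANOVA and "Post-hoc analysis, if necessary". A separate general line reads "Continuous Variables: Mann-Whitney U test, One-way ANOVA". The section closes with "Unless otherwise specified, all statistical tests will be conducted at a two-sided significance level of 0.05". It names neither a post-hoc method nor a single primary test.

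**The concern.** Two things are at stake.

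- **Clarity.** The section that governs the analysis does not carry over the level set in the sample-size section, and it makes the pairwise tests conditional on an unstated trigger. An observed difference can therefore fall where the conclusion depends on which level is used. The wording touches all three contrasts. In practice it bears mainly on DST vs DST+OSMS, which has the smallest planned difference (4.6 days) and is the only test of whether OSMS adds to DST.
- **Efficiency.** Even with 0.0167 settled, Bonferroni is stricter than three arms require. The same family-wise protection is available with each pair at 0.05 behind an overall test, and the contrast that gains most is the one with the least power.

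**Working it through.** **Inputs (6.2).** Means 20.8, 14.6 and 10.0 days, so the differences are 6.2 (control vs DST), 10.8 (control vs DST+OSMS) and 4.6 (DST vs DST+OSMS). SD 7.19; 56 per arm; two-sided 0.0167; 80% power; 10% dropout.

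**Step 1: the plan's own figure.** For 4.6 days at two-sided 0.0167 and 80% power, the normal approximation gives 52 per group and the noncentral t gives 53. Dividing by the Mann-Whitney efficiency under normality gives 53/0.955 = 55.5, rounded up to 56, which matches the plan. For dropout, 56/0.9 = 62.2, rounded up to 63, and 3 × 63 = 189, which also matches. Section 6.2 does not name the test, so Mann-Whitney is an inference. Of the methods tried, only this one gave 56, and it rests on DST vs DST+OSMS at 0.0167.

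**Step 2: where the level decides the result.** The standard error of a difference is 7.19 × √(2/56) = 1.359 days. The smallest significant observed difference is t × 1.359. For a t-test (110 df):

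- at 0.0167: 2.43 × 1.359 = 3.30 days
- at 0.05: 1.98 × 1.359 = 2.69 days

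With the one-way ANOVA error (165 df) these are 3.29 and 2.68. The band of about 2.7 to 3.3 days assumes that the observed SD is exactly 7.19.

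**Step 3: how often that happens under the planned means (normal data).**

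| Contrast and test | Power at 0.0167 | Power at 0.05 | Difference |
|---|---|---|---|
| DST vs DST+OSMS, t-test | 0.828 | 0.919 | 0.091 |
| DST vs DST+OSMS, one-way ANOVA contrast | 0.832 | 0.920 | 0.088 |
| DST vs DST+OSMS, Mann-Whitney | 0.804 | 0.904 | 0.100 |
| Control vs DST, t-test | 0.983 | 0.995 | 0.012 |

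Control vs DST+OSMS is practically never affected. If the true DST vs DST+OSMS difference is smaller than planned, the t-test share is 13.5% at 2 days, about 17.6% at 3 days and 13.6% at 4 days (assumed range).

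**Step 4: family-wise error under the global null (simulation, 56 per arm).**

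- Each pair at 0.0167: 4.4%
- Tukey: 5.0%
- Overall F test at 0.05, then pairs at 0.05: 5.0%
- Kruskal-Wallis, then Mann-Whitney, at 0.05: 4.9%
- Three ungated tests at 0.05: 12.2%

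**Step 5: why the gate suffices with three arms.** If any two of the three pairwise nulls are true, all three arms are equal. The closed family therefore contains only the global null and the three single pairs. At most one pair can be null when the global null is false, and that pair is tested at 0.05. The simulation agrees: with one pair equal and the third arm far away, the error on the equal pair is 0.050 (ANOVA contrast) and 0.0495 (Mann-Whitney).

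**Step 6: what the closed procedure gains.** Under the planned means the overall test is practically always significant, so the gate costs nothing. Power for DST vs DST+OSMS is then the 0.05 column of Step 3: 0.832 rises to 0.920 (ANOVA contrast). In eight other non-null mean patterns tried by simulation, power for each true difference was never lower than under Bonferroni. This concerns power over repeated trials and does not hold for every dataset. If the third mean lies midway between the other two, F = t²/2. A pair with t between 2.42 and √(2 × 3.05) = 2.47 then passes Bonferroni but not the F test.

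**The case against.** The strongest case against is that 6.2 already settles the matter. It does more than choose a sizing input: it names the three comparisons, states the hypotheses and says that the correction is applied. The 0.05 default in 8.4.2 yields to anything specified elsewhere. This stands, and 0.0167 governs on the natural reading.

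A reader might go further and infer that the primary contrasts will be tested ungated at 0.05, with a family-wise error of about 12%. The documents do not support that. It requires setting 6.2 aside, and it is the least natural of the readings that 8.4.2 allows. A gated step or an adjusted post-hoc test would also fit the 8.4.2 bullet, and both control the error. Nor does 8.4.2 single out DST vs DST+OSMS; the emphasis comes only from the planned means.

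Two technical limits also stand.

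- The band of 2.7 to 3.3 days moves with the observed SD. Over its 95% sampling range of about 6.2 to 8.1, the band runs from 2.3–2.9 to 3.0–3.7 days. Mann-Whitney has no fixed threshold in mean days.
- The normal model is imperfect: with mean 10.0 and SD 7.19, about 8% of DST+OSMS durations would be negative (z = −10.0/7.19 = −1.39). With positive skewed data of the same means and SD (an assumption), the Mann-Whitney share between the two levels falls from 10% to 4.7% (gamma) or 1.9% (lognormal), because power at 0.0167 is already 0.92 or 0.97. The t-test share barely changes (8.4% to 8.9%).

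Finally, Bonferroni is valid, and replacing it can be called a preference. That is fair as to validity. The replacement is still worth proposing because it gains power at the same sample size and error rate, at a small and known cost.

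**Conclusion.** The point holds as an improvement to the design, with a clarity gap attached. No error inflation has been shown. Section 8.4.2 should state the rule for the primary contrasts, but on its own that is a minor clarification.

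The substantive finding is that plain Bonferroni costs about 9 percentage points of power on DST vs DST+OSMS (0.83 against 0.92) compared with a closed procedure that keeps family-wise error at about 5%. This rests on the planned means, SD 7.19, 56 evaluable infants per arm, normal data and a one-way ANOVA contrast. For Mann-Whitney the gain is 0.80 to 0.90 under normality and may be much smaller with skewed data. The gain is about 1 point for control vs DST and practically nil for control vs DST+OSMS.

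**What to change.** In both 6.2 and 8.4.2, replace Bonferroni for the primary outcome with a closed procedure, for example:

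*The three SOF-FOF hypotheses are tested by a closed procedure. An overall three-group test is done at two-sided 0.05. Only if it is significant is each pair tested, at two-sided 0.05. All other tests use two-sided 0.05 without adjustment for multiplicity and are labelled so.*

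Name one matching pair of tests:

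- the one-way ANOVA F test with its pairwise contrasts (168 − 3 = 165 error df), not the two-way or repeated-measures ANOVA now listed for the primary outcome; or
- Kruskal-Wallis with pairwise Mann-Whitney tests.

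In either case, remove the primary outcome from the two-way and repeated-measures bullet, and delete the conditional qualifier on post-hoc analysis for these contrasts. Make the change before any between-group comparison of the primary outcome is run.

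**Cost.** The sample size stays at 56 per group and 189 in total. Section 6.2 must be amended, and the simultaneous confidence intervals that match Bonferroni are lost. Intervals at 98.33% can still be reported but may disagree with the test.

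**If the sponsor keeps Bonferroni.** Add a sentence to 8.4.2 pointing to 6.2 for the three primary contrasts, and name the pairwise test. Nothing else changes.

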6.4 Inclusion and Exclusion criteria for enrolment

6.4.1. Inclusion criteria

- (1) Preterm infants with a gestational age of less than 32+0 weeks.
- (2) Infants currently receiving sufficient tube feeding (at least 120 ml/kg/day).
- (3) Infants who can be treated with heated, humidified high-flow nasal cannula (HFNC) within 33+0 weeks.
- (4) Infants who only have feeding-related issues remaining, with no need for special medical treatment.
- (5) Infants whose parents voluntarily sign the informed consent form for participation in the study.

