6.4.2. Exclusion criteria

- (1) Infants with major congenital malformations, such as those affecting the face, central nervous system, gastrointestinal system, or heart.
- (2) Infants with gastrointestinal complications.
- (3) Infants with chronic medical conditions, such as Grade 3 or higher intraventricular hemorrhage (according to the classification by Papile et al), periventricular leukomalacia, or those who have undergone surgical treatment for necrotizing enterocolitis.

7. Study procedures

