7.3.3 Discontinuation of intervention

The intervention will be discontinued when the infant can feed orally without requiring special treatment (including apnea, bradycardia, and oxygen desaturation) for two consecutive days during all feedings.

- If the infant is disrupted by factors such as taking sedatives or undergoing ophthalmologic exams

Protocol_DST and OSMS_oral feeding performance

within 30 minutes prior to the intervention, the intervention will not be applied that day.

- During the intervention, if any hemodynamic instability, apnea, bradycardia, or oxygen desaturation that does not resolve spontaneously occurs, the intervention will be stopped early. The intervention will only resume once the infant has stabilized and returned to a stable condition.

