8.4 Statistical analysis methods

8.4.1. Definition of Analysis Sets

- ITT Analysis Set (Intent-to-Treat): Includes data from all pediatric patients who received at least one session of oral rehabilitation therapy and had at least one assessment of the outcome variable.
- FAS Analysis Set (Full Analysis Set): Includes data from the ITT set, excluding patients who did not meet the eligibility criteria or failed to undergo the primary outcome assessment.
- PP Analysis Set (Per-Protocol): Includes data from the ITT set, specifically from patients who strictly adhered to the clinical trial protocol by completing direct swallowing training or both direct swallowing training and sensory-motor stimulation therapy, with outcome variables assessed.

This study will conduct ITT, FAS, and PP analyses, with FAS analysis being the primary approach.

* Subgroup Analysis: Subgroup analysis will be performed based on gestational age, birth weight, and bronchopulmonary dysplasia.

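### Section 9 turns three clinical setbacks into dropout from the trial with no follow-up rule, so affected infants can be lost from the primary FAS comparison

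*Combined protocol and SAP*

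**What the plan says.** The list in section 9 is titled as criteria for dropping out of the clinical trial. Its first item is a guardian's request or withdrawal of consent. The other three are clinical events:

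- respiratory deterioration "requiring the use of a respiratory device beyond nasal positive pressure ventilation";
- "gastrointestinal deterioration during the trial period, necessitating fasting for more than 48 hours";
- "When a serious adverse event occurs". Serious adverse event is not defined anywhere, and no limit of time or relatedness is attached.

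Rules for the intervention itself stand elsewhere. Section 7.3.3 says when it ends, when a day's session is skipped and when a session is cut short: "The intervention will only resume once the infant has stabilized and returned to a stable condition".

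The primary outcome (8.3.1) runs from the first oral feed to full oral feeding free of side effects that need special treatment. Section 8.1 lists the feeding milestones to be recorded. It makes no exception for dropouts, and it does not say that recording continues after dropout.

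Section 8.4.1 makes the FAS the primary set. It is the ITT set, "excluding patients who did not meet the eligibility criteria or failed to undergo the primary outcome assessment". The ITT set itself takes only infants who had at least one therapy session and "had at least one assessment of the outcome variable".

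**The concern.** Only withdrawn consent obliges the investigators to stop observing a child. Respiratory escalation, a long fast or a serious adverse event may be good reasons to stop the intervention, but the infant's date of full oral feeding can usually still be observed. If trial staff read section 9 literally and close the record, an infant with such an event between the first oral feed and full oral feeding has no primary outcome value, and the FAS rule then removes that infant.

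Infants with these setbacks plausibly take longer to reach full oral feeding than those who stay. Losing them makes an arm look faster than it was. The comparison between arms is biased if the proportion lost, or the prognosis of those lost, differs by arm. The 10% dropout allowance in 6.2 protects precision; it does nothing about selective loss.

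**Working it through.** **1. The route from event to exclusion.** Section 7.3.3 acts on the intervention; section 9 acts on trial participation. Section 8.1 plans the milestone dates but does not require them after dropout. Under 8.4.1 an infant with no primary assessment is outside the FAS. The ITT set does not repair this: it is not primary, it also needs an outcome assessment, and 8.4.2 gives no rule for a missing value. So such an infant *can* be lost. Nothing says that the infant *must* be.

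**2. The plan's own figures (6.2).** Inputs: means of 20.8, 14.6 and 10.0 days, SD 7.19, two-sided alpha 0.05/3 = 0.0167, power 80%. The smallest contrast is 14.6 − 10.0 = 4.6 days. A t test needs 53 per group. The usual Mann-Whitney adjustment gives 53 × π/3 = 55.5, hence 56, as stated. Then 56/0.90 = 62.2, hence 63 per arm and 3 × 63 = 189, as stated. The allowance is 63 − 56 = 7 infants per arm for all causes, including guardian withdrawal.

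**3. Size of the shift.** Let p be the proportion of an arm lost through clinical events and e the excess days of those lost over those retained. The retained mean is the full-arm mean minus p × e. With no true effect, the observed difference (A − B) is

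shift = −(pA × eA − pB × eB),

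which with equal e has size |pA − pB| × e.

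The documents give no rate for these events, so the inputs below are assumptions. Differences of 2 and 5 points correspond to 0.02 × 63 = 1.3 and 0.05 × 63 = 3.2 infants per arm. They would arise, for example, if total loss were 12% vs 8% or 15% vs 5% (averaging the planned 10%) and half of it were clinical.

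The false-positive rate is the rejection probability of a two-sample t test for one pairwise comparison, with 56 per arm, alpha 0.0167 and standard error 7.19 × √(2/56) = 1.36 days. SD is held at 7.19, which is a simplification.

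| Difference in clinical loss | Excess of those lost | Shift (days) | Share of 4.6 days | False-positive rate |
|---|---|---|---|---|
| 0, equal prognosis | any | 0 | 0% | 1.67% |
| 2 points | 0.5 SD (3.595) | 0.07 | 2% | 1.7% |
| 2 points | 1 SD (7.19) | 0.14 | 3% | 1.7% |
| 2 points | 2 SD (14.38) | 0.29 | 6% | 1.9% |
| 5 points | 0.5 SD | 0.18 | 4% | 1.8% |
| 5 points | 1 SD | 0.36 | 8% | 2.0% |
| 5 points | 2 SD | 0.72 | 16% | 3.2% |

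Equal rates alone do not guarantee a zero shift. With 5% lost in each arm, but 2 SD excess in one and 1 SD in the other, the shift is 0.05 × (14.38 − 7.19) = 0.36 days.

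**4. The opposite direction.** If the shift works against a true 4.6-day effect, the detectable difference is 4.6 minus the shift. With 56 per arm, t-test power falls from 83% to 80% (0.14 days), 75% (0.36) or 66% (0.72).

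**The case against.** The strongest reply is that section 9 is silent on follow-up and does not forbid it. The FAS rule removes infants without a primary assessment; it does not remove dropouts as such. The outcome is a routine NICU date, already listed in 8.1, so a dropped infant whose date was recorded stays in the FAS under the current wording. This is right, and it rules out one reading a reader might infer: that the plan orders these infants out of the analysis. What remains is that a rule titled as trial dropout, with no instruction to continue, leaves the matter to whoever applies it.

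The second reply is that the events should be few and balanced. Enrolment is limited to "Infants who only have feeding-related issues remaining, with no need for special medical treatment", and "Infants with gastrointestinal complications" are excluded, as are severe intraventricular haemorrhage, periventricular leukomalacia and surgically treated necrotising enterocolitis. The intervention starts only after 48 hours off nasal CPAP and at 120 ml/kg/day or more by gavage (7.3.1), so both named thresholds are high. Randomisation is stratified by gestational age and sex. The screen and the 15-minute sham for controls (section numbered 10.4.3.3) limit arm-dependent decisions, although the overview and section 5 also call the study open-label. A setback before the first oral feed may delay the start without lengthening the interval, and an adverse event after full oral feeding cannot touch the primary outcome. All of this stands and reduces the risk. It does not remove it: masking the decision does not equalise true event rates between arms, and the plan itself anticipates the events.

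A reader might also infer a seriously inflated type I error. With 15% vs 5% lost, every loss clinical and a 2 SD excess, the shift would be 0.10 × 14.38 = 1.44 days and the false-positive rate 8.9%. The documents do not support that case. The 10% allowance includes guardian withdrawal, nothing points to a threefold imbalance, and a 14.38-day excess is larger than the whole assumed DST + OSMS mean of 10.0 days.

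**Conclusion.** The point holds as a weakness in a stated rule that should be corrected. It does not show that the result will be biased. Section 9 treats three clinical events as dropout from the trial, no text secures the outcome afterwards, and the primary FAS omits infants without it.

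On assumed differences in clinical loss of 2 to 5 points and a 1 SD excess, the effect is small: 0.14 to 0.36 days and a false-positive rate of 1.7% to 2.0% against 1.67%. It reaches 0.72 days and 3.2% at 5 points and 2 SD, and it is zero if loss and prognosis are equal across arms. These figures rest on assumed rates and excesses, a t test with 56 per arm, and constant SD. The direction is unknown, so the documents do not support a claim that the loss favours the interventions. Nor do they show that the planned method of analysis must be replaced.

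**What to change.** 1. **Section 9.** Restate the three clinical items as criteria for stopping the study intervention, and let only withdrawal of consent end follow-up. Define serious adverse event. Which clinical action each event calls for remains a matter for the sponsor's clinicians.
2. **Follow-up.** State that the feeding milestones in 8.1 continue to be recorded for all other randomised infants, who are analysed in the assigned arm.
3. **Section 8.4.1.** State that no infant is excluded from the ITT set or the FAS because the intervention was stopped under section 9.
4. **Reporting.** Give section 9 events, and infants without a date of full oral feeding, by arm and reason.

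The cost is amendment wording in two sections and a reporting table; the milestone dates are already planned NICU data. The downside is that retained infants who received little intervention slightly dilute the estimated effect. If data collection is complete, recovering the milestone dates where possible, amending 8.4.1 and reporting by arm remain useful.

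A time-to-event analysis with death as a competing event, and rules for transfer, discharge or never starting oral feeding, are optional sensitivity analyses. They would depart from the planned comparison of means and are not needed to resolve this point.
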